7.3 Subject Population(s) for Analysis

- All-treated population: Any subject entered into the study started the drug infusion and/or biopsy procedure.
- Protocol-compliant population: Any subject who was entered and received the protocol required study drug exposure and required protocol processing
- All-completed population: Only subjects who completed ALL study related procedures and follow-up will be included.

8 Safety and Adverse Events

Safety Review Plan –Study progress and safety will be reviewed quarterly with the research fellow and study coordinator and, because these are relatively small studies, the data summarized at 6 month intervals to allow for a large enough sample to assess outcomes. Progress reports, including patient recruitment and AE's will be provided to the Endocrine Research Committee following each of the 6 month reviews in the event that no participants are accrued in the study a report will not be provided. An annual report will be compiled and will include a list and summarization of adverse events at the time of the non-competing renewal. In addition, the annual report will address (1) whether adverse event rates are consistent with pre-study assumptions; (2) reason for dropouts from the study; (3) whether all participants met entry criteria; (4) whether continuation of the study is justified on the basis that additional data are needed to accomplish the stated aims of the study. The annual report will be reviewed by the Endocrine Research Committee and the results included in the minutes. These will be forwarded to the IRB and NIDDK and, if applicable, the Mayo CTSA CRU and FDA as indicated.

8.1 Definitions

Unanticipated Problems Involving Risk to Subjects or Others (UPIRTSO)

Any unanticipated problem or adverse event that meets the following three criteria:

- Serious: Serious problems or events that results in significant harm, (which may be physical, psychological, financial, social, economic, or legal) or increased risk for the

subject or others (including individuals who are not research subjects). These include: (1) death; (2) life threatening adverse experience; (3) hospitalization - inpatient, new, or prolonged; (4) disability/incapacity - persistent or significant; (5) birth defect/anomaly; (6) breach of confidentiality and (7) other problems, events, or new information (i.e. publications, DSMB reports, interim findings, product labeling change) that in the opinion of the local investigator may adversely affect the rights, safety, or welfare of the subjects or others, or substantially compromise the research data, **AND**

- Unanticipated: (i.e. unexpected) problems or events are those that are not already described as potential risks in the protocol, consent document, not listed in the Investigator's Brochure, or not part of an underlying disease. A problem or event is "unanticipated" when it was unforeseeable at the time of its occurrence. A problem or event is "unanticipated" when it occurs at an increased frequency or at an increased severity than expected, **AND**
- Related: A problem or event is "related" if it is possibly related to the research procedures.

Adverse Event

An untoward or undesirable experience associated with the use of a medical product (i.e. drug, device, biologic) in a patient or research subject.

Serious Adverse Event

Adverse events are classified as serious or non-serious. Serious problems/events can be well defined and include;

- death
- life threatening adverse experience
- hospitalization
- inpatient, new, or prolonged; disability/incapacity
- persistent or significant disability or incapacity
- birth defect/anomaly

and/or per protocol may be problems/events that in the opinion of the sponsor-investigator may have adversely affected the rights, safety, or welfare of the subjects or others, or substantially compromised the research data.

Other important medical events are those that may not be immediately life threatening, but are clearly of major clinical significance. They may jeopardize the subject, and may require intervention to prevent one of the other serious outcomes noted above.

All adverse events that do not meet any of the criteria for serious, should be regarded as **non-serious adverse events**.

Adverse Event Reporting Period

For this study, the follow-up period is up to 6 weeks from the 1st biopsy visit. Any adverse event occurring during the course of the study period will be reported.

Preexisting Condition

A preexisting condition is one that is present at the start of the study. A preexisting condition should be recorded as an adverse event if the frequency, intensity, or the character of the condition worsens during the study period.

General Physical Examination Findings

At screening, any clinically significant abnormality should be recorded as a preexisting condition. At the end of the study, any new clinically significant findings/abnormalities that meet the definition of an adverse event must also be recorded and documented as an adverse event.

Post-study Adverse Event

All unresolved adverse events should be followed by the sponsor-investigator until the events are resolved, the subject is lost to follow-up, or the adverse event is otherwise explained. At the last scheduled visit, the sponsor-investigator should instruct each subject to report, to the sponsor-

investigator, any subsequent event(s) that the subject, or the subject's personal physician, believes might reasonably be related to participation in this study.

Abnormal Laboratory Values

Research lab results taken between study drug administration and study completion are expected to be abnormal as a result of adipose tissue and muscle biopsies (catecholamines) done during the study. Screening lab values are reviewed by the physician principal investigator in the EMR and documented as reviewed in the EMR. Clinical lab results obtained by a primary care provider or other physician that is not involved in the study in the time that a participant receives the study drug will not be assessed for abnormality.

Hospitalization, Prolonged Hospitalization or Surgery

Any adverse event that results in hospitalization or prolonged hospitalization should be documented and reported as a serious adverse event unless specifically instructed otherwise in this protocol. Any condition responsible for surgery should be documented as an adverse event if the condition meets the criteria for an adverse event.

Neither the condition, hospitalization, prolonged hospitalization, nor surgery are reported as an adverse event in the following circumstances:

- Hospitalization or prolonged hospitalization for diagnostic or elective surgical procedures for a preexisting condition. Surgery should **not** be reported as an outcome of an adverse event if the purpose of the surgery was elective or diagnostic and the outcome was uneventful.
- Hospitalization or prolonged hospitalization required to allow efficacy measurement for the study.
- Hospitalization or prolonged hospitalization for therapy of the target disease of the study, unless it is a worsening or increase in frequency of hospital admissions as judged by the clinical investigator.

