1.5 Risks and Benefits

Radiation: Radiation exposure from the studies supported by this grant include the radiation from the dual energy x-ray absorptiometry, and computed tomography scans of the abdomen.

Blood sampling: Blood samples are collected from an indwelling intravenous catheter for this study. Bruising can occur with venipuncture, as can fainting.

Infusion of substrates: We will infuse minute quantities of glucose and palmitate that are labeled with stable isotopes as part of these studies. The quality assurance plans for these compounds are reviewed and approved by the Mayo Clinic Radioactive Drug Research Committee as the designated representative of the FDA. We will also infuse insulin intravenously and give local anesthetics for the tissue biopsies. The insulin is infused using clinical safeguards as well as research pharmacy safeguards under an IND exemption from the Mayo IRB.

Adipose and muscle biopsies: The risks of these procedures include pain, hematomas, bruising, infection, and scarring of the biopsy site.

Insulin infusion: The risk of insulin infusion is hypoglycemia.

Niacin: the risk of niacin infusion is flushing, pruritus, nausea or vomiting.

2 Study Objectives

Primary Objective

To assess the effect of overnight suppression of FFA with intravenous niacin on trafficking of FFA into intramyocellular ceramides and/or DG

Secondary Objective

To assess the effect of overnight suppression of FFA with intravenous niacin on insulin signaling and insulin-stimulated muscle glucose uptake

3 Study Design

This study is a non-randomized, niacin vs. saline control trial of the effects of niacin on intracellular fatty acid trafficking in insulin resistant states. Subjects will be screened at outpatient clinic visit appointments and interested qualified subjects will be consented and offered participation in this trial. Once consent has been obtained baseline values will be established and subjects will begin treatment and follow-up for up to the next 8 weeks.

A final evaluation and collection of lab samples will be conducted at the end of the study.

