8.2 Recording of Adverse Events

At each contact with the subject, the study team will seek information on adverse events by specific questioning and, as appropriate, by examination. Information on all adverse events will be recorded immediately in the source document, and also in the appropriate adverse event section of the case report form (CRF) or in a separate adverse event worksheet. All clearly related signs, symptoms, and abnormal diagnostic, laboratory or procedure results will be recorded in the source document.

Adverse events are considered events that are not already described as routine research risks in the consent form. We will not report pain at time of the biopsy as an AE, nor will we report bruising from biopsy or line placement procedures as these are nearly guaranteed to occur with all participants. All adverse events occurring during the study period will be recorded. The clinical course of each event would be followed until resolution, stabilization, or until it has been ultimately determined that the study treatment or participation is not the probable cause. Serious adverse events that are still ongoing at the end of the study period must be followed up, to determine the final outcome. Any serious adverse event that occurs during the Adverse Event Reporting Period and is considered to be at least possibly related to the study treatment or study participation will be recorded and reported immediately.

We will use the following standardized system for classification and grading of Adverse Events
http://evs.nci.nih.gov/ftp1/CTCAE/CTCAE_4.03_2010-06-14_QuickReference_8.5x11.pdf

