- A. Protection of Subject Privacy – As part of the screening for these studies a medical history and physical examination will be performed, blood tests and body composition measurements will be made. None of the research data will be entered into the Mayo Electronic Medical Record. Any paper records that are generated are kept in [name] laboratory, which is locked at all times to prevent hallway entry. Because it often takes several months from the initial volunteer contact until the studies are complete, and because we need to communicate with multiple units (Radiology, Nuclear Medicine, Mayo CTSA CRTU, etc.) over the course scheduling, it is not possible to de-identify paperwork immediately. The paperwork with patient identifiers is kept in a locked room when not in use. Whenever possible the paper records generated will be such that once the study is complete the identifiers can be removed. A paper matching the subject name and other identifying information with the subject code should be kept in a separate place from the study information. No information will be given to anyone without permission from the subject. If samples are sent outside Mayo for analysis they are de-identified per Mayo Biospecimens Committee rules.
- B. Database Protection – Electronic research data will be kept on password protected computer servers that can be accessed only by those with human studies/privacy training and only with [name] direct approval. Electronic communication with outside collaborators involves only unidentifiable information.
- C. Confidentiality during AE Reporting –AE reports and annual summaries will not include participant-identifiable material. Each will include the identification code only.

IV. Adverse Event Information

- A. Definition - An adverse event (AE) is any untoward medical occurrence in a subject temporally associated with participation in the clinical study. An adverse finding can

include a sign, symptom, abnormal assessment (laboratory test value, vital signs, electrocardiogram finding, etc.) or any combination of these.

A Serious Adverse Event (SAE) is any adverse event that results in one or more of the following outcomes:

- Death
- A life-threatening event
- Inpatient hospitalization or prolongation of existing hospitalization
- A persistent or significant disability/incapacity
- A congenital anomaly or birth defect
- Important medical event based upon appropriate medical judgment

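### Section 8.1 attributes every on-study research lab abnormality to the biopsies, which contradicts the sampling schedule and the protocol's own adverse event rules

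*Combined protocol and SAP*

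**What the plan says.** Section 8.1, under Abnormal Laboratory Values, makes three statements.

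- On research samples: "Research lab results taken between study drug administration and study completion are expected to be abnormal as a result of adipose tissue and muscle biopsies". The mechanism given in parentheses is catecholamines. No analyte, threshold or time of draw is named.
- On screening: "Screening lab values are reviewed by the physician principal investigator in the EMR and documented as reviewed in the EMR".
- On outside results: "Clinical lab results obtained by a primary care provider or other physician that is not involved in the study", when they fall "in the time that a participant receives the study drug will not be assessed for abnormality".

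Other sections treat laboratory abnormalities as adverse event (AE) material.

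- Section 8.1, AE reporting period: "Any adverse event occurring during the course of the study period will be reported". The follow-up period is up to 6 weeks from the first biopsy visit.
- Section 8.2: clearly related "abnormal diagnostic, laboratory or procedure results will be recorded in the source document".
- Section 8.3.1, Relationship Index: the sponsor-investigator grades each event's relation to the drug, and several grades explicitly cover laboratory abnormalities.
- Section 10.1, IV.A: an adverse finding can include an "abnormal assessment (laboratory test value, vital signs, electrocardiogram finding, etc".

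Two further statements concern on-study results. Section 10.1, IV.E expects abnormal labs to be discovered only at screening. The data review tables in 9.3 and 10.1 have the research fellow and principal investigator review out-of-range research results as they arrive, with a footnote about detecting laboratory problems.

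On risk, section 1.5 says: "The risk of insulin infusion is hypoglycemia".

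**The concern.** The rule assigns a cause before any value is seen. It covers the whole period from first drug exposure to the end of the study, although a biopsy cannot explain a value drawn before it. It also leaves staff without a usable instruction, because different sections say that on-study abnormalities are expected, are found only at screening, are reviewed as they arrive, and may be adverse findings.

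What is at stake is safety classification. The AE worksheet in 8.3.1 asks whether an event was expected. The unanticipated-problem definition in 8.1 depends partly on what the protocol already describes. The annual report compares AE rates with pre-study assumptions. An abnormality labelled in advance as expected and biopsy-related may not reach any of these steps. The clearest example is low glucose: insulin-treated participants with diabetes receive insulin overnight, and everyone undergoes a 5-hour insulin clamp.

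**Working it through.** The plan gives no figure to reproduce. The check is clock arithmetic on the schedule, followed by a comparison of sections.

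**Inputs.** Section 6.2 gives the infusion start (2100 h), the overnight samples (2200, 2400, 0200, 0400 h), a series at 0830–0900 h, and the first muscle biopsy after that series, with an adipose biopsy at the same time. Section 3.1 gives the clamp start (0915 h), its length (5 h) and the second biopsy at its end. The Schedule of Events puts Visit 2 at day 28–56. (Section 3.1 prints 1200 where 6.2 has 2400; the later steps do not depend on this.)

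**Visit 1 timing.**

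| Sample | Hours after 2100 h | Biopsy already taken? |
|---|---|---|
| 2200 h | 1 | No |
| 2400 h | 3 | No |
| 0200 h | 5 | No |
| 0400 h | 7 | No |
| 0830–0900 h | 11.5–12 | No |
| Clamp, 0915 h to about 1415 h | 12.25–17.25 | Yes, first biopsy |

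Every scheduled Visit 1 sample in the first 12 hours on drug precedes any biopsy, so the stated cause cannot apply to it. Overnight glucose monitoring in insulin-treated participants falls in the same window. The clamp readings follow the first biopsy; timing does not refute the attribution there, but case-by-case grading still conflicts with it.

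**Visit 2 timing.** The window runs to study completion, which section 6 places at Visit 2. The overnight samples there precede that visit's biopsies and follow the Visit 1 biopsies by about 28 to 56 days (4 to 8 weeks).

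**AE period against visit window.** 6 weeks × 7 = 42 days from the first biopsy visit, while Visit 2 may fall on day 56. 56 − 42 = 14 days, so the AE period can end up to two weeks before the last visit.

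**Sections side by side.**

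- 8.1 fixes the cause for a whole class of results; 8.3.1 requires a cause to be judged for each event.
- 8.1 expects abnormal on-study results; 10.1, IV.E says abnormal results would surface only at screening. Both cannot hold.
- 10.1, IV.E also does not fit the review of out-of-range research results in 9.3 and 10.1. That review might fill the gap, but its footnote describes finding analytical or experimental faults and does not mention participant safety.
- 8.2 and 10.1, IV.A allow a laboratory value to be recorded or to count as an adverse finding; 8.1 gives no rule for when an expected abnormality becomes one.

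**The case against.** The strongest reply is that the text is loosely worded but harmless. Much of this stands.

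- A reader might infer that the protocol refuses to assess clinical labs in general. It does not. The exclusion covers only results from providers outside the study, and only while the participant receives study drug. That is part of one monitored inpatient stay, whether the infusion ends at 0900 h (6.2) or 1420 h (3.1). Screening labs are reviewed.
- A reader might infer that hypoglycemia would be written off. The documents do not say so. Expecting abnormality is not a ban on recording, section 8.1 also commits to reporting any AE in the study period, and clamp glucose is measured every 10 minutes and acted on. Section 8.2 names only biopsy pain and procedure bruising as unreported. Its separate clause on routine risks in the consent form raises a different question, which cannot be judged without that form.
- No laboratory harm of niacin is named. The listed effects are flushing, pruritus, nausea and vomiting, and the pre-biopsy draws mainly serve fatty acid and tracer measurements.
- Counting clamp glucose readings would not measure the problem: they are routine readings, not missed events, and the documents do not say whether they are research lab results.
- The conflict with 8.2 and 10.1, IV.A is limited, since 8.2 covers clearly related results and IV.A says only that a laboratory value can be an adverse finding.

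None of this rescues the attribution itself. The schedule contradicts it, and the protections cited sit in sections that disagree with 8.1 and with each other.

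**Conclusion.** The point holds as an internal contradiction in safety reporting. Section 8.1 assigns a biopsy cause to results that, on the protocol's own schedule, precede any biopsy at Visit 1 or follow the previous one by 4 to 8 weeks. It also conflicts with case-by-case causality grading and with the statement that abnormal labs appear only at screening. Followed literally, it could pre-class a drug- or insulin-related abnormality, such as a low overnight glucose in a participant on insulin, as expected and biopsy-related. The documents support "could" in that sentence's plain sense, and not that such events will go unrecorded.

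The size is qualitative: all scheduled samples in the first 12 hours on drug at Visit 1, plus the Visit 2 overnight samples. No number of missed events can be derived. Sample size, power and alpha are unaffected. The glucose example assumes that overnight and clamp glucose count as research lab results, a term the protocol leaves undefined. The change should be made, because it is cheap and the present wording cannot be applied consistently.

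**What to change.** Reconcile 8.1, 8.2, the Relationship Index in 8.3.1, the data review table and footnote in 9.3 and 10.1, and parts IV.A and IV.E of 10.1. Specifically:

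1. Delete the blanket attribution in 8.1.
2. State that the investigator reviews on-study values, explicitly including overnight and clamp glucose, for clinical significance, together with any outside clinical results the team receives.
3. Run that review through study completion rather than to the end of the 6-week AE period, which can close before a day-56 Visit 2.
4. Record clinically significant values as AEs under the definition already in 10.1, IV.A, with cause judged case by case on the 8.3.1 scale.
5. If a biopsy presumption is kept, limit it to named catecholamine-responsive research analytes drawn after a biopsy on the same day, and exclude glucose from it.
6. Correct the statement in 10.1, IV.E about screening, and say whether the review of out-of-range research results also serves safety.

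The cost is protocol wording and a brief investigator review of values already collected. No sampling or analysis changes.

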8.2 Recording of Adverse Events

At each contact with the subject, the study team will seek information on adverse events by specific questioning and, as appropriate, by examination. Information on all adverse events will be recorded immediately in the source document, and also in the appropriate adverse event section of the case report form (CRF) or in a separate adverse event worksheet. All clearly related signs, symptoms, and abnormal diagnostic, laboratory or procedure results will be recorded in the source document.

Adverse events are considered events that are not already described as routine research risks in the consent form. We will not report pain at time of the biopsy as an AE, nor will we report bruising from biopsy or line placement procedures as these are nearly guaranteed to occur with all participants. All adverse events occurring during the study period will be recorded. The clinical course of each event would be followed until resolution, stabilization, or until it has been ultimately determined that the study treatment or participation is not the probable cause. Serious adverse events that are still ongoing at the end of the study period must be followed up, to determine the final outcome. Any serious adverse event that occurs during the Adverse Event Reporting Period and is considered to be at least possibly related to the study treatment or study participation will be recorded and reported immediately.

We will use the following standardized system for classification and grading of Adverse Events
http://evs.nci.nih.gov/ftp1/CTCAE/CTCAE_4.03_2010-06-14_QuickReference_8.5x11.pdf

